10.12.8. Safety Assessments

During the Continued Access Period, all AEs, SAEs, and mirikizumab exposure will be reported on the CRF. SAEs will also be reported to the sponsor. In the event that an SAE occurs, the sponsor may request additional information to evaluate the reported SAE.

Investigators will perform any other standard procedures, and tests needed to treat and evaluate participants; however, the choice and timing of the tests will be at the investigator's discretion. The sponsor will not routinely collect the results of these assessments.

See Sections 10.12.1, and Sections 8.2 and 8.3 for more details.

10.12.9. Permitted Concomitant Medications/Therapies during Continued Access

Note: At the discretion of the investigator, any permitted concomitant medication may have the dose modified, be discontinued, or be re-started during the Continued Access Period. If there are any questions on these permitted medications, please contact the medical monitor.

	-
Drug Class (examples)	Comments
Oral corticosteroids or oral budesonide (standard or extended-release formulation [budesonide MMX]) for UC • prednisone mg/day or equivalent • budesonide MMX mg/day, or • beclomethasone dipropionate mg/day (gastro-resistant prolonged-release tablet)	Short courses of corticosteroids, including budesonide, are permitted with tapering to begin as soon as clinically feasible, with a goal of discontinuing within 3 months. Participants who require increasing doses and repeated courses or are intolerant to tapering of corticosteroids should be considered for treatment discontinuation and termination from the Continued Access Period
Corticosteroids for non-UC indications	Permitted as follows:
	continued use to treat adrenal insufficiency
	locally administered use, e.g., inhaled, intranasal, intraarticular, and topical
	single doses (oral or IV) corticosteroids as premedication for miri self-administered CCI and
	limited use for acute conditions per investigator discretion
Rectally administered corticosteroids (enemas or suppositories)	Permitted with the goal of tapering as soon as clinically feasible or discontinuing within 3 months. Participants who require continuous use of steroid enemas or suppositories or are intolerant to tapering should be considered for treatment discontinuation and early termination from the Continued Access Period
Immunomodulators for UC	Permitted
(oral AZA, 6-MP, or methotrexate)	
Oral 5-ASAs (mesalamine, balsalazide,	Permitted
olsalazine) and sulfasalazine for UC	
Rectally administered 5-ASAs	Permitted
(enemas or suppositories)	Da
Topical JAK inhibitors and calcineurin inhibitors	Permitted
Antidiarrheals	Permitted
(loperamide, diphenoxylate with atropine)	1 omittee
Low-dose or baby aspirin (75 to 162.5 mg)	Daily use for cardiovascular prophylaxis permitted
Non-live vaccines	Permitted
(killed, inactivated, subunit, or RNA-based)	
Complementary alternative medicine for UC and non-UC indications	Permitted

(dietary/herbal supplements, vitamins,	
probiotics)	

Abbreviations: 5-ASA = 5-aminosalicylic acid; 6-MP = 6-mercaptopurine; AZA = azathioprine; IV = intravenous; JAK = Janus kinase; MMX = Multi-matrix system; UC = ulcerative colitis.

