10.12. Appendix 12: Optional Continued Access Period

10.12.1. Overview

The Continued Access Period is offered to sites with eligible study participants who complete AMBZ Study Periods I to III.

The duration of the Continued Access Period will differ by participant and country.

Efficacy data will not be collected during the Continued Access Period. Participants will continue to be followed for safety throughout their participation in this Continued Access Period.

Study activities and procedures described in this appendix are in addition to the requirements of the main AMBZ protocol, unless otherwise specified. Some information from the main AMBZ protocol is repeated for clarity.

^a Participants who are eligible for Continued Access should move directly from Visit 10 to Visit 501, on the same day, if possible. Visit 801 should not be performed.

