- 68. Have been diagnosed with a condition, underwent a surgical procedure, received prohibited treatment, or experienced a laboratory abnormality that met criteria for permanent discontinuation from mirikizumab treatment prior to Visit 501 of the Continued Access Period. See Section 7.1.
- 69. Currently meet temporary discontinuation of study intervention criteria (see Section 7.1.4). Note: Once resolution of the condition or appropriate treatment is met, the participant may be eligible for the Continued Access Period if the maximum roll-over period to enter the Continued Access Period has not been exceeded.
- 70. Have initiated a new prohibited medication (see Section 10.11) prior to Visit 501 of the Continued Access Period.
- 71. Have had evidence of alcohol dependence or illicit drug abuse prior to Visit 501 of the Continued Access Period.
- 72. Have had the presence of a hepatic or hematologic laboratory abnormality prior to Visit 501 of the Continued Access Period, that would require permanent discontinuation from mirikizumab treatment. See Section 7.1.
- 73. Have an underlying disease, or surgical, physical, or medical condition that, in the opinion of the investigator, would potentially affect participant safety within the continued access period.
- 74. Have a known systemic hypersensitivity to any component of mirikizumab, or have experienced an acute systemic hypersensitivity event with previous mirikizumab treatment administration, that precludes mirikizumab treatment.
- 75. Are pregnant or planning pregnancy (females only) while enrolled in the continued access period, or within weeks after receiving the last dose of mirikizumab.
- 76. Became part of the investigator site personnel directly affiliated with this study or their immediate families prior to Visit 501 of the Continued Access Period.
- 77. Became a Lilly employee or an employee of third-party organizations involved with the study prior to Visit 501 of the Continued Access Period.
- 78. Have enrolled in any other clinical study involving an investigational product or any other type of medical research judged not to be scientifically or medically compatible with this study.

79. Are unsuitable for inclusion in the continued access period in the opinion of the investigator or sponsor for any reason that may compromise the subject's safety.

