10.12.10 Prohibited Concomitant Medications/Therapies during Continued Access

This section outlines medications that are prohibited during the continued access period of the study. Use of the medications in this table is allowed at the discretion of the investigator after a participant discontinues study intervention and completes the DC visit.

Drug Class (examples)	Continued Access Period Comments and Guidelines
Biologics, JAK inhibitors, Immunomodulators	
Anti-TNF antibodies	Prohibited
(adalimumab, golimumab, infliximab)	
CCI	Prohibited
Anti-integrin antibodies	Prohibited
(vedolizumab)	
CCI	Prohibited
Small-molecule S1P receptor modulator (ozanimod)	Prohibited
Immunomodulatory medications, oral or IV:	Prohibited
Cyclosporine, mycophenolate mofetil, thalidomide, tacrolimus.	
Other immunomodulatory medications should be discussed with	
medical monitor prior to use	
Corticosteroids	
Oral corticosteroids for UC	Initiation or increase above the oral dose
	at screening is prohibited
IV corticosteroids for UC	Course of IV corticosteroids prohibited
Systemic corticosteroids for non-UC indication, oral or IV	Prohibited
Allowed exceptions: See Section 10.12.9.	
Other	
Agents depleting B or T cells	Prohibited
(alemtuzumab, rituximab, visilizumab)	
Any investigational therapy, biologic or non-biologic	Prohibited
Rectally administered investigational preparations for UC (arsenic)	Prohibited
Interferon therapy	Prohibited
Leukocyte apheresis, leukapheresis	Prohibited
(Adacolumn)	
Bacillus Calmette-Guerin (BCG) vaccination	Use prohibited, also CCI after last dose
T'	of mirikizumab
Live or attenuated vaccines	Use prohibited, also c after last dose
(for measles, mumps, rubella, or varicella. See Section 6.8.3.)	of mirikizumab

Abbreviations: DC = discontinue; IL= Interleukin; IV = intravenous; M = month; S1P = Sphingosine-1-phosphate; TNF = tumor necrosis factor; UC = ulcerative colitis.

[figure not shown]

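### Protocol 10.12.9 permits short oral corticosteroid courses for UC in Continued Access while 10.12.10 prohibits starting one, and nothing visible reconciles the two rows

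*Protocol*

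**What the plan says.** Two tables in Protocol Appendix 12 govern concomitant medication in the Continued Access Period.

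- **Permitted (10.12.9).** The row covers oral corticosteroids, and oral budesonide in standard or extended-release form, for UC. It says: "Short courses of corticosteroids, including budesonide, are permitted with tapering to begin as soon as clinically feasible". The aim is to stop within 3 months. Participants who need rising doses and repeated courses, or who cannot tolerate tapering, "should be considered for treatment discontinuation and termination from the Continued Access Period". A note above the table says that, at the investigator's discretion, "any permitted concomitant medication may have the dose modified, be discontinued, or be re-started during the Continued Access Period".
- **Prohibited (10.12.10).** The row for oral corticosteroids for UC begins "Initiation or increase above the oral dose", and the cell goes on to say that this, relative to screening, is prohibited. The sentence above the table says use of the listed drugs is "allowed at the discretion of the investigator after a participant discontinues study intervention and completes the DC visit". Two rows further down, systemic corticosteroids for non-UC indications carry the pointer "Allowed exceptions: See Section 10.12.9". The UC row has no pointer.

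Protocol 10.12.1 says of the appendix as a whole: "Study activities and procedures described in this appendix are in addition to the requirements of the main AMBZ protocol, unless otherwise specified". That relates the appendix to the main protocol. It does not rank the two tables against each other.

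**The concern.** The two rows share a drug class, an indication and a study period, yet one permits what the other prohibits. A site that consults only one table would see nothing to query.

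The consequence for mirikizumab also differs. Under 10.12.9, stopping is something to consider, and only after rising and repeated courses or failed tapering. The sentence above the 10.12.10 table places use of listed drugs after study intervention has been discontinued. In the main protocol, Section 6.8.2 makes discontinuation mandatory for anyone who requires a prohibited drug for UC. Section 7.1, which 10.12.7 carries into Continued Access by name, lists lack of benefit or worsening disease that requires a drug prohibited under 10.11.

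The same course could therefore count as permitted treatment at one site and as prohibited medication, with possible discontinuation, at another. That bears on participant management, on what is recorded as a protocol deviation (SAP 4.1.5), and on the disposition summary in the Continued Access safety analysis (SAP 4.1.3).

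**Working it through.** The point is textual and the plan gives no figure to reproduce. The check sets the rows side by side for each type of participant. Let *d* be the oral corticosteroid dose at screening and *C* the dose limit in the 10.12.9 row, which is redacted.

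**Step 1: participant on none at screening (*d* = 0).** Protocol 10.11 restricts starting oral corticosteroids for UC in the main study. Criterion 70 in 10.12.5.2 excludes from Continued Access those who "Have initiated a new prohibited medication (see Section 10.11) prior to Visit 501 of the Continued Access Period". An eligible participant with *d* = 0 therefore reaches Visit 501 without having started one, and a first course is an initiation. Any positive dose also exceeds zero. The 10.12.10 row prohibits the course whether the words about the screening dose qualify the increase only or both the initiation and the increase. The 10.12.9 row permits it as a short course. The redacted limit cannot remove the conflict, because every positive dose is above zero.

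**Step 2: which drugs.** Protocol 10.10 uses the heading of oral corticosteroids for UC for prednisone or equivalent, budesonide MMX and beclomethasone, so Step 1 covers those. Standard-formulation budesonide is unclear: 10.12.9 permits it, 10.11 gives it a row of its own, and 10.12.10 shows no such row.

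**Step 3: participant on a corticosteroid at screening (*d* > 0).**

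| Course in Continued Access | 10.12.9 | 10.12.10 | Conflict? |
|---|---|---|---|
| Above *d*, up to *C* | permitted | prohibited | only if *C* > *d* |
| Re-start at or below *d* after the Period III taper (6.8.1) | permitted | depends on parsing | only if the screening-dose words do not also qualify initiation |

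For the first line, the conflicting band is *d* < dose ≤ *C*. Criterion 10 in Protocol 5.1 limits *d* to 20 mg/day prednisone or equivalent. If *C* were the same 20 mg/day (an assumption), the band would be 20 − 20 = 0 mg/day wide at *d* = 20 and 20 − 10 = 10 mg/day wide at *d* = 10.

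**Step 4: does anything visible resolve Step 1?**

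- The note in 10.12.9 covers modifying, stopping and re-starting. It does not mention a first start or refer to 10.12.10.
- Reading 10.12.9 as limited to courses already running fails. The row speaks of short and repeated courses, and it names standard budesonide, which 10.11 prohibits in Periods II and III.
- The exception pointer "Allowed exceptions: See Section 10.12.9" is on the non-UC row only.

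**Step 5: illustrative count.** The documents supply only the planned enrolment of about 160. The three shares below are assumptions: none at screening (0.50 to 0.80), entering Continued Access (0.50 to 0.90), and starting an oral course there (0.05 to 0.20).

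- Low: 160 × 0.50 × 0.50 × 0.05 = 2.0
- High: 160 × 0.80 × 0.90 × 0.20 = 23.0

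**The case against.** The strongest defence of the text is that the rows address different things. In 10.12.10 the row for intravenous corticosteroids prohibits a course, while the oral row speaks of initiation or increase. One could take the oral row to bar new or raised ongoing therapy, with the time-limited short course in 10.12.9 as a specific allowance. The protocol says this nowhere, so sites would have to infer it, and the need for clarification stands.

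Other objections carry more weight:

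- **Consequence for mirikizumab.** Section 6.8.2 points to 10.11 and requires an early discontinuation visit, which the main study defines for stopping before Visit 10. Continued Access has its own discontinuation visit and Visit 901, and 10.12.7 imports Section 7.1 by name but not 6.8.2. The general clause in 10.12.1 can carry 6.8.2 over, so discontinuation under it is possible but not certain. The additional list in 10.12.7 is not public and may settle this.
- **Scope.** The conflict is firm only for the drugs in Step 2 and participants with *d* = 0. The Step 3 cases depend on a redacted limit or an ambiguous modifier.
- **Impact.** Continued Access is optional and collects no efficacy data (Protocol 10.12.1), and the SAP plans only a basic safety analysis for it. Sections 6.8 and 10.12.9 send questions to the medical monitor, and 6.8.2 says a prohibited UC drug should not be withheld where that would compromise safety. These limit the harm but do not supply a rule.

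**Conclusion.** The concern holds. For a participant on no oral corticosteroid at screening, a first course of prednisone or equivalent, budesonide MMX or beclomethasone for UC in Continued Access is permitted by 10.12.9 and prohibited by 10.12.10. This rests on visible wording and does not depend on any redacted value. The conflicts for participants with a positive screening dose are conditional, and the effect on mirikizumab is subject to the unseen part of 10.12.7.

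The number affected is unknown. The range of 2 to 23 follows entirely from the assumed shares and shows only that the group need not be empty. The Week 12 primary endpoint is not affected. This should be fixed because it bears on how participants are managed and how their disposition is recorded, but it does not threaten the main analysis.

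**What to change.** Reconcile the rows for oral corticosteroids for UC in 10.12.9 and 10.12.10 so that a single rule applies. The reconciled text should make clear:

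- how it treats a first course in a participant on none at screening;
- how it treats a re-start after the Period III taper;
- whether the 10.12.10 row covers standard-formulation budesonide;
- what follows for study intervention, consistently with Sections 6.8.2 and 7.1, unless the non-public list in 10.12.7 already does this.

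Which clinical rule applies is for the sponsor's clinicians to decide. The cost is a protocol amendment or a clarification letter to sites, with no new data or procedures.

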10.12.10 Prohibited Concomitant Medications/Therapies during Continued Access

This section outlines medications that are prohibited during the continued access period of the study. Use of the medications in this table is allowed at the discretion of the investigator after a participant discontinues study intervention and completes the DC visit.

Drug Class (examples)	Continued Access Period Comments and Guidelines
Biologics, JAK inhibitors, Immunomodulators	
Anti-TNF antibodies	Prohibited
(adalimumab, golimumab, infliximab)	
CCI	Prohibited
Anti-integrin antibodies	Prohibited
(vedolizumab)	
CCI	Prohibited
Small-molecule S1P receptor modulator (ozanimod)	Prohibited
Immunomodulatory medications, oral or IV:	Prohibited
Cyclosporine, mycophenolate mofetil, thalidomide, tacrolimus.	
Other immunomodulatory medications should be discussed with	
medical monitor prior to use	
Corticosteroids	
Oral corticosteroids for UC	Initiation or increase above the oral dose
	at screening is prohibited
IV corticosteroids for UC	Course of IV corticosteroids prohibited
Systemic corticosteroids for non-UC indication, oral or IV	Prohibited
Allowed exceptions: See Section 10.12.9.	
Other	
Agents depleting B or T cells	Prohibited
(alemtuzumab, rituximab, visilizumab)	
Any investigational therapy, biologic or non-biologic	Prohibited
Rectally administered investigational preparations for UC (arsenic)	Prohibited
Interferon therapy	Prohibited
Leukocyte apheresis, leukapheresis	Prohibited
(Adacolumn)	
Bacillus Calmette-Guerin (BCG) vaccination	Use prohibited, also CCI after last dose
T'	of mirikizumab
Live or attenuated vaccines	Use prohibited, also c after last dose
(for measles, mumps, rubella, or varicella. See Section 6.8.3.)	of mirikizumab

Abbreviations: DC = discontinue; IL= Interleukin; IV = intravenous; M = month; S1P = Sphingosine-1-phosphate; TNF = tumor necrosis factor; UC = ulcerative colitis.

[figure not shown]
10.13. Appendix 13: Country-specific Requirements

[figure not shown]
For sites in EU member states

This appendix is not applicable at this time.

For sites outside of EU member states

Country-specific requirements, if any, will be described in a separate protocol addendum.

10.15. Appendix 15: Abbreviations and Definitions

Term	Definition
6-МР	6-mercaptopurine
abuse	Use of a study intervention for recreational purposes or to maintain an addiction or dependence
ADA	anti-drug antibody
AE	adverse event
AESI	adverse event of special interest
AIDS	acquired immunodeficiency syndrome
ALP	alkaline phosphatase
ALT	alanine aminotransferase
Anti-HBc	Antibodies to hepatitis B core antigen
AST	aspartate aminotransferase
authorized IMP	Applicable to the EU only: a medicinal product authorized in accordance with Regulation (EC) No 726/2004 or in any Member State concerned in accordance with Directive 2001/83/EC, irrespective of changes to the labeling of the medicinal product, which is used as an investigational medicinal product
AZA	azathioprine
BCG	Bacillus Calmette-Guerin
C difficile	Clostridioides difficile
CD	TΔ~–,, β) < -β≥xβ≥
CDC	Centers for Disease Control and Prevention
CFR	Code of Federal Regulations
CIOMS	Council for International Organizations of Medical Sciences
СК	creatine kinase
complaint	A complaint is any written, electronic, or oral communication that alleges deficiencies related to the identity, quality, purity, durability, reliability, safety or effectiveness, or performance of a drug or drug delivery system
compliance	Adherence to all study-related, good clinical practice (GCP), and applicable regulatory requirements

Term	Definition	
CRF	case report form; a printed, optical, or electronic document designed to record all of the protocol-required information to be reported to the sponsor for each trial participant	
CRP	clinical research physician: individual responsible for the medical conduct of the study. Responsibilities of the CRP may be performed by a physician, clinical research scientist, global safety physician, or other medical officer	
CCI		
СТА	Clinical Trial Agreement	
CTR	Clinical Trial Regulation	
CXR	Chest X-ray	
D.Bil	Direct bilirubin	
Device deficiencies	equivalent to product complaint	
ECAV	extended continued access visit	
ECG	electrocardiogram	
ED	early discontinuation	
EDC	electronic data capture	
EIM	extraintestinal manifestation	
enroll	The act of assigning a participant to a treatment. Participants who are enrolled in the study are those who have been assigned to a treatment	
enter	Participants entered into a study are those who sign the informed consent form directly or through their legally acceptable representatives	
ERB	Ethical Review Board	
ES	endoscopic subscore	
FSH	follicle stimulating hormone	
CCI		
GCP	good clinical practice	
GGT	gamma-glutamyl transferase	
HBsAg	hepatitis B surface antigen	
HBV	hepatitis B Virus	

Term	Definition	
HCV	hepatitis C Virus	
HIV	human immunodeficiency virus	
IB	Investigator's Brochure	
CCI		
ICF	informed consent form	
ICH	International Council for Harmonisation	
IEC	Independent Ethics Committee	
IL	interleukin	
IMP	Investigational Medicinal Product (see also "investigational product") A medicinal product which is being tested or used as a reference, including as a placebo, in a clinical trial	
informed consent	A process by which a participant voluntarily confirms their willingness to participate in a particular study, after having been informed of all aspects of the study that are relevant to the participant's decision to participate. Informed consent is documented by means of a written, signed, and dated informed consent form	
INR	international normalized ratio	
interim analysis	An interim analysis is an analysis of clinical study data, separated into treatment groups, that is conducted before the final reporting database is created or locked	
investigational product	A pharmaceutical form of an active ingredient or placebo being tested or used as a reference in a clinical trial, including products already on the market when used or assembled (formulated or packaged) in a way different from the authorized form, or marketed products used for an unauthorized indication, or marketed products used to gain further information about the authorized form. See also "IMP"	
IRB	Institutional Review Board	
IV	intravenous	
IWRS	interactive web-response system	
JAK	Janus Kinase	
LTBI	latent tuberculosis infection	

Term	Definition	
medication error	Errors in the prescribing, dispensing, or administration of a study intervention, regardless of whether or not the medication is administered to the participant or the error leads to an AE. Medication error generally involves a failure to uphold 1 or more of the 5 "rights" of medication use: the right participant, the right drug, the right dose, right route, at the right time.	
	In addition to the core 5 rights, the following may also represent medication errors:	
	dose omission associated with an AE or a product complaint	
	dispensing or use of expired medication	
	use of medication past the recommended in-use date	
	dispensing or use of an improperly stored medication	
	 use of an adulterated dosage form or administration technique inconsistent with the medication's labeling (for example, Summary of Product Characteristics, IB, local label, and protocol), or 	
	shared use of cartridges or prefilled pens, or both	
Misuse	Use of a study intervention for self-treatment that either is inconsistent with the prescribed dosing regimen, indication, or both, or is obtained without a prescription	
MMS	Modified Mayo Score	
MMX	multi matrix colonic delivery technology	
MTX	methotrexate	
NRS	numeric rating scale	
PA	posterior—anterior	
Participant	Equivalent to CDISC term "subject": an individual who participates in a clinical trial, either as recipient of an investigational medicinal product or as a control	
PC	product complaint	
PCR	polymerase chain reaction	
PGA	Physician's Global Assessment	
CCI		
PK	Pharmacokinetics	
PRO/ePRO	patient-reported outcomes or electronic patient-reported outcomes	
PT	Prothrombin Time	

Term	Definition
Q4W	once every 4 weeks
CCI	
QoL	quality of life
RB	rectal bleeding
RNA	ribonucleic acid
S1P	Sphingosine-1-phosphate
SAE	serious adverse event
SAP	statistical analysis plan
SC	Subcutaneous
Screen	The act of determining if an individual meets minimum requirements to become part of a pool of potential candidates for participation in a clinical study
SDAL	Study Drug Administration Log
SF	stool frequency
SoA	Schedule of Activities
SUSAR	suspected unexpected serious adverse reaction
ТВ	tuberculosis
TBL	total bilirubin level
TEAE	Treatment-emergent adverse event: An untoward medical occurrence that emerges during a defined treatment period, having been absent pretreatment, or worsens relative to the pretreatment state, and does not necessarily have to have a causal relationship with this treatment
TNF	tumor necrosis factor
UC	ulcerative colitis
ULN	upper limit of normal
UNRS	urgency numeric rating scale
UV	unscheduled visit
WBC	white blood cell
WHO	World Health Organization

Term	Definition
WNOCBP	women not of childbearing potential
WOCBP	women of childbearing potential
CCI	

